10.1.3. Analysis of the secondary endpoints

The total Quality of Life (DLQI) score from Visit 2 and 3 will be analysed by a linear mixed model similar to the model for the primary endpoint, except that the random interaction effect of product and subject is not included, as there is only one measurement per subject for each product.

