5.2.2. Secondary endpoint

The Secondary endpoint is a health-related quality of life measured by the (DLQI) score evaluated at the end of each test period (scale from 0-30). See appendix 2.

5.2.3. Exploratory endpoints:

[REDACTED]

Safety assessments:

- Adverse events
- Device deficiencies
- Concomitant medication

See appendix 3 for questions used as basis for the above endpoints and assessments.

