5.3. Rationale for selection and measurement of endpoints

The primary endpoint as well as [REDACTED] endpoints are subjective and objective parameters assessing the condition of the peristomal skin; and are essential to investigate whether [REDACTED] can reduce peristomal skin complications induced by leakage of fecal output.

To evaluate the performance of the test product, the Decision Tree score will be applied. This score is the outcome of a modified version of the Ostomy Skin Tool 1.0.⁶ The new skin tool, referred to as Ostomy Skin Tool 2.0 (manuscript in preparation), is comprised of a patient-reported outcome (PRO) questionnaire and an automated image analysis conducted via an artificial intelligence algorithm⁷. The PRO consists of six items designed to assess the severity of peristomal skin complications (appendix 4). The Decision Tree score captures both visual and non-visual signs of peristomal skin complications and assigns patients to a skin severity level based on the observed combination of these variables as outlined in appendix 1. The Decision Tree score successfully underwent a psychometric validation process; thereby, concluding that the Decision Tree score is a valid and reliable method for evaluating the peristomal skin condition in clinical trials (manuscript in preparation).

The Dermatology Life Quality Index (DLQI) will be used in this investigation (appendix 2) and is a validated, dermatology specific quality of life tool. The subject will complete a paper version of the DLQI at each study visit for the purpose of evaluating their health-related quality of life during each study period.

Adverse events and device deficiencies will be collected to ensure safety.

⁶ Martins, L., et al. *The ostomy skin tool: tracking peristomal skin changes*. Br J Nurs. 2010; 19(15): p. 960, 932-4.

⁷ Andersen, N.K., et al., *Automated Assessment of Peristomal Skin Discoloration and Leakage Area Using Artificial Intelligence*. *Frontiers in Artificial Intelligence*, 2020. 3(72).

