7.5. Schedule of Assessments

Assessment	Screening visit (V0)	Visit 1 (V1)	Every baseplate change	Visit 2 (V2)	Visit 3 (V3)	Telephone call (Weeks 1, 3, 6, and 8)
Informed consent	X					
Inclusion and exclusion criteria	X					
Pregnancy test (urine dipstick)	X					
Randomisation	X					
Subjects trained in skin preparation, Clinical Trial App, and Investigational product use according to IFU.	X	X		X		
Assessment of subject's wellbeing and compliance with CIP	X	X		X	X	X
Subject to take photos and complete questions in App			X			
Subject to complete QoL		X		X	X	
Complete eCRFs		X		X	X	
Dispense Investigational product according to randomisation		X		X		
Subject remuneration (if applicable)		X		X	X	

Assessment	Screening visit (V0)	Visit 1 (V1)	Every baseplate change	Visit 2 (V2)	Visit 3 (V3)	Telephone call (Weeks 1, 3, 6, and 8)
Confirm future visit and follow-up calls with subject	X	X		X		
Deviations	X	X		X	X	
Adverse Events		X		X	X	X
Device Deficiencies		X		X	X	X
Concomitant Medications	X	X		X	X	X

Table 1: Schedule of Assessments

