10.1.1. Definition of analysis populations

Intention to Treat (ITT), Safety and Per Protocol (PP) populations will be defined at a formal data review meeting before database lock. As a minimum, the data manager, the clinical manager and the statistician will be involved in the classification of subjects.

The ITT population (full analysis set) will be constituted by all randomised subjects with valid informed consent who have been exposed to at least one product, with information on at least one product with respect to either primary or secondary endpoints.

The PP population will constitute a subset of ITT subjects:

- who fulfill the inclusion/exclusion criteria
- where the primary endpoint, the decision tree score, is present in at least one of the steady state periods

- who have not used another product other than the randomized product for more than 3 days in a row at steady state
- who do not have a major deviation, as defined in section 13.0. Any exclusion of subjects from the PP/ITT population must be documented. Invalid individual data points may be omitted from analysis even though the corresponding subject is part of the ITT or PP population. Any exclusion of data points will be documented.

The Safety population will constitute by subjects who have given informed consent.

All statistical analysis will be based upon the ITT and PP population whereas adverse events and device deficiencies will be assessed based on the safety population.

Considering the data obtained it might be considered to make additional explorative analyses based on a subset of the ITT/PP population.

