combined model). Hence 33, 1-piece and 33, 2-piece users will be needed to complete the study. In case there are no significant difference between type of product the 66 users will be analysed in a reduced model. If the true difference is only 0.2 then 66 subjects should ensure a power of 82% to detect the difference as significantly different from zero but still within the 95% confidence interval for the clinically relevant difference. To take a potential drop-out (20%) into account it is recommended to include a total of 41 1-piece and 41 2-piece users, resulting in a total of 82 subjects.

If the recruitment target of 82 subjects is not reached within the timelines, the recommendation is to prolong the timelines to reach the recruitment target. This is to avoid a situation of not showing a significant result due to the power being too low.

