Appendix 2: Dermatology Life Quality Index Questionnaire

(<https://www.cardiff.ac.uk/medicine/resources/quality-of-life-questionnaires/dermatology-life-quality-index>)

The aim of this questionnaire is to measure how much your skin problem has affected your life
OVER THE LAST WEEK. Please tick one box for each question.

[figure not shown]
1. Over the last week, how **itchy, sore, painful or stinging** has your skin been?
Very much A lot A little Not at all
2. Over the last week, how **embarrassed** or **self conscious** have you been because of your skin?
Very much A lot A little Not at all
3. Over the last week, how much has your skin interfered with you going **shopping** or looking after your **home** or **garden**?
Very much A lot A little Not at all Not relevant
4. Over the last week, how much has your skin influenced the **clothes** you wear?
Very much A lot A little Not at all Not relevant
5. Over the last week, how much has your skin affected any **social** or **leisure** activities?
Very much A lot A little Not at all Not relevant
6. Over the last week, how much has your skin made it difficult for you to do any **sport**?
Very much A lot A little Not at all Not relevant
7. Over the last week, has your skin prevented you from **working** or **studying**?
If "No", over the last week how much has your skin been a problem at **work** or **studying**?
Yes No Not relevant
A lot A little Not at all Not relevant
8. Over the last week, how much has your skin created problems with your **partner** or any of your **close friends** or **relatives**?
Very much A lot A little Not at all Not relevant
9. Over the last week, how much has your skin caused any **sexual difficulties**?
Very much A lot A little Not at all Not relevant
10. Over the last week, how much of a problem has the **treatment** for your skin been, for example by making your home messy, or by taking up time?
Very much A lot A little Not at all Not relevant

© AV Fulayek GK Khan, April 1992, www.terminology.org.uk, this must not be copied without the permission of the authors.

Please check you have answered EVERY question. Thank you.

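### No DLQI is planned when a subject leaves the trial, so early leavers have no secondary endpoint on the product they left, and the earliest fall outside ITT

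*Combined protocol and SAP*

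**What the plan says.** - **Collection.** Section 5.3: "The subject will complete a paper version of the DLQI at each study visit". Table 1 (section 7.5) has the row "Subject to complete QoL" marked at V1, V2 and V3. The table has no early-withdrawal column.
- **Analysis.** Section 10.1.3: "The total Quality of Life (DLQI) score from Visit 2 and 3 will be analysed by a linear mixed model". It drops the product-by-subject random effect because "there is only one measurement per subject for each product". V1 precedes the first study product, so the one value per product is the one at the end of its period.
- **Withdrawal.** Section 6.5 lets a subject leave at any time and asks for no final questionnaire. Section 7.4 covers unplanned visits, but only for adverse events and device deficiencies.
- **Stopping the test product but staying in.** Section 5.1 lets a subject who cannot finish a period on the test product use their own product for the rest of it, with documentation.
- **Primary endpoint window.** The Decision Tree score counts at steady state only (5.2.1), and steady state starts after two weeks of use (5.1).
- **ITT.** Section 10.1.1 requires randomisation, valid consent and exposure, together "with information on at least one product with respect to either primary or secondary endpoints".
- **Drop-out.** Section 10.2 sets enrolment at 82 "To take a potential drop-out (20%) into account". It says nothing about when or why subjects leave.

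**The concern.** Subjects who leave because their skin is worse, or the product is hard to live with, probably have the poorest DLQI on that product. The plan has no occasion to record that score. A period 1 leaver contributes no on-product DLQI. A period 2 leaver contributes a score only for the product completed, not for the one left. The DLQI comparison then leans towards subjects who tolerated what they were given.

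The mixed model cannot repair this. It can borrow from a subject's other period, but it has no observation on the product being left. The only missing-data sensitivity analysis (section 10.1.2) concerns the primary endpoint and restricts to subjects observed in both periods, so it moves further from the leavers. None is planned for DLQI.

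The ITT rule adds to this. Section 6.4 removes a wrongly randomised subject from ITT only if untreated and without endpoint data. Section 10.1.1, read literally, also removes an eligible, treated subject who leaves before steady state in period 1.

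**Working it through.** **1. The plan's drop-out figure.** 66 / (1 - 0.20) = 82.5, and 33 / 0.80 = 41.25 per product type. The plan uses 82 and 41, so its figure reproduces. Expected drop-outs: 0.20 × 82 = 16.4, about 16.

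**2. What each leaver contributes under the plan.**

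| When the subject leaves the trial | Decision Tree score at steady state | On-product DLQI | In ITT (literal 10.1.1) |
|---|---|---|---|
| Period 1, first 14 days | none | none | no |
| Period 1, days 15-35 | first product | none | yes |
| Period 2 | first product, perhaps second | first product only | yes |
| Stops test product, stays in (5.1) | depends on timing | a V2 or V3 score exists | yes, if that visit is completed |

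The first row assumes that Decision Tree scores from before steady state are not primary endpoint information, which follows from the definition in 5.2.1.

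**3. How many.** Timing is not given. Assume drop-out is even over 70 days:
- first 14 days: 16.4 × 14/70 = 3.3, about 3 outside ITT (4% of 82);
- days 15-35: 16.4 × 21/70 = 4.9, about 5 with primary data but no on-product DLQI;
- period 1 in total: 16.4 × 35/70 = 8.2, about 8 (10%) with no on-product DLQI.

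If half of all drop-outs fall in the first two weeks, about 8 are outside ITT. If all do, about 16 (20%).

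**4. Possible effect on the DLQI estimate.** The documents give no DLQI mean, SD, effect or drop-out pattern, so every input here is assumed.
- Model: intercept, product, period and random subject, fitted by generalised least squares to expected values. Within-subject correlation 0.5, SD 5.
- Completers: 66, with comparator 8 and test 6 (difference -2).
- Leavers from test: equal numbers per period, DLQI 8 on comparator where observed.

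For 8 test leavers at DLQI 13, four per period:
- As planned: 66 pairs at -2, plus four comparator-only scores at the completers' mean. Estimate -2.00 (SE 0.61).
- With exit scores: the four comparator-first leavers become pairs at 13 - 8 = +5. The pairs alone give (66 × -2 + 4 × 5)/70 = -112/70 = -1.60. The four test-only scores of 13 pull this to -1.43 (SE 0.59).

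| Leavers (assumed) | Reported as planned | With exit DLQI | Overstatement |
|---|---|---|---|
| 8 from test at 13 | -2.00 | -1.43 | 2.00/1.43, about 40% |
| 4 from test at 13 | -2.00 | -1.70 | about 18% |
| 4 from test at 10 | -2.00 | -1.83 | about 9% |
| 2 from test at 13 | -2.00 | about -1.85 | about 8% |
| 16, 8 from each product, at 13 on the product left | -2.00 | -1.84 | about 9% |

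In the last row, leavers from the comparator have DLQI 6 on test where it is observed. In the first row, correlations of 0.3 and 0.7 give -1.35 and -1.51, and adding the planned period-by-product term leaves -1.43. Changing the SD at fixed correlation alters only the SE. What matters is how many leave, from which product, and how poor their scores are.

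**The case against.** The best case for the plan has four parts.

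- **Stakes.** Section 10.4 rests pass or fail on the primary endpoint alone. This stands and sets the priority, although the secondary objective does rest on DLQI.
- **Definition.** The secondary endpoint is the score at period end, and a day-5 score is a different quantity. This stands too. It is why an exit score belongs in a sensitivity analysis and not in the main one.
- **Size.** The larger bias figures need leaving to be concentrated on the test product. Balanced or milder leaving gives -1.70 to -1.85. This stands. The 40% is one adverse scenario, not an estimate.
- **Existing safeguards.** App entries are made at every baseplate change (7.3), and adverse events and deficiencies are checked at unplanned visits (7.4). Only the DLQI form is missing.

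A reader might also infer three stronger things that the documents do not support:

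- *That DLQI is taken only at Visits 2 and 3.* It is also taken at V1. That score comes before study product, so it does not fill the gap.
- *That anyone who stops a product early has no secondary endpoint and leaves ITT.* Section 5.1 lets subjects stop the test product and stay in, with a V2 or V3 score. Their problem is attribution: the form (Appendix 2) asks about symptoms "OVER THE LAST WEEK. Please tick one box for each question", so the later score may describe their own product, and 10.1.3 has no rule for it.
- *That early product failures are hidden.* These subjects remain in the safety population, and any exclusion from ITT must be documented (10.1.1). What is lost is their efficacy information.

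**Conclusion.** The gap is real but limited. The plan provides no DLQI at withdrawal, so a subject who leaves the trial before a period-end visit has no secondary endpoint on the product in use. The literal ITT rule also excludes randomised, exposed subjects who leave in the first two weeks of period 1. With even drop-out that is about 3 subjects outside ITT and about 8 without any on-product DLQI; both counts rest on an assumed timing.

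The direction of any bias depends on why subjects leave. If poor experience with the test product drives it, the DLQI benefit is overstated, by roughly 8% to 40% in the scenarios tried, all on assumed inputs and taking the exit score as the product's value. The plan as written cannot show where in that range the trial lies, and a score not taken at exit cannot be recovered. The primary conclusion is not called into question on this ground. This is a cheap improvement of minor priority.

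**What to change.** 1. **Table 1 and section 6.5:** add a DLQI at the contact where a subject withdraws from the trial. Add one also at the point where a subject switches to their own product under section 5.1, recording which product it refers to.
2. **Section 10.1.3:** keep the V2/V3 analysis as the main one. Add an ITT sensitivity analysis in which the withdrawal or switch score is used as that product's value. Report the number of leavers by product and period beside it.
3. **Section 10.1.1:** let this score count as secondary endpoint information, so that exposed early leavers who supply it stay in ITT.

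The cost is one paper form per leaver or switcher and one extra model run. There are two limits. The scores are earlier than day 35 and, for very early leavers, the one-week recall may reach back before the study product. Subjects lost to follow-up will not supply a form, so their number should still be reported.

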10.1.4. Analysis of exploratory endpoints

10.1.5. Analyses of safety endpoints

Adverse events will be listed and summarized, if relevant. Device deficiencies and concomitant medication will be listed.

10.2. Sample size

The Decision Tree (DT) score will be calculated at each baseplate change. A Severe score is equal to 3 whereas Moderate is 2, Mild is 1 and Not treatment required is 0. It is assumed that data are distributed in all 4 categories and therefore can be analysed by a model assuming normally distributed data.

The sample size calculation is based on a simplified linear mixed model with no effect of product type and no period effect. The model includes a fixed effect of product (comparator and test product), a random effect of subject and a random interaction effect of product and subject. As the sample size does not distinguish between product type it is assumed that both 1- and 2-piece users uses approximately 10 baseplates in the steady state period. This means, the power of the analysis might be in favour of 1-piece users if the final model is not combined as 1-piece users might use more products.

Based on data (PP population) from the previous CP288 investigation, it is assumed that the total standard deviation of the primary endpoint is 1.1 and that the total variation 1.1² is divided so that:

- a random effect of subject accounts for 46% of the total variation
- a random interaction effect of product and subject accounts for 9%
- and the residual accounts for 45% of the total variation

In the below table the needed sample size is calculated by simulation for varying values of the true difference between comparator and test product regarding mean DT score and for different values of the power to demonstrate that the difference is significantly different from 0.

Table 2: Subjects needed for comparing mean DT score (scale 0-3) between two products

True Difference	Reduction in mean if the mean for the comparator is 2.0 as for [REDACTED] in CP288	Power			
		0.8	0.85	0.9	0.95
0.2	10%	64	>70	>70	>70
0.3	15%	30	35	40	50
0.4	20%	<20	20	24	30
0.5	25%	<20	<20	<20	20

Based on interpolation between the numbers in the table, 33 subjects should test each product to ensure a power of 96%, if the true difference between the comparator product and a test product is 0.4 (clinically relevant difference according to the validation of the DT score). Correspondingly, 33 subjects will ensure a power of 83% if the true difference is 0.3 (still within the 95% confidence interval for the clinically relevant difference according to the validation of the DT score). 1-piece and 2-piece users will be evaluated separately (in a

combined model). Hence 33, 1-piece and 33, 2-piece users will be needed to complete the study. In case there are no significant difference between type of product the 66 users will be analysed in a reduced model. If the true difference is only 0.2 then 66 subjects should ensure a power of 82% to detect the difference as significantly different from zero but still within the 95% confidence interval for the clinically relevant difference. To take a potential drop-out (20%) into account it is recommended to include a total of 41 1-piece and 41 2-piece users, resulting in a total of 82 subjects.

If the recruitment target of 82 subjects is not reached within the timelines, the recommendation is to prolong the timelines to reach the recruitment target. This is to avoid a situation of not showing a significant result due to the power being too low.

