4.8. Total number of investigational products intended for the clinical investigation

The subjects will be included for $35^{-1/3}$ days per test period, for approximately 70 days.

Subjects using 1-piece products are expected to change their products every day. Therefore, they are expected to use approximately 35 test products and 35 comparator products during their participation.

Subjects using 2-piece products are expected to change their products every two-three days. Therefore, they are expected to use approximately 20 test product baseplates and 20 comparator baseplates during their participation. Subjects using 2-piece products will be supplied with enough bags for the duration of the investigation.

5. Design of the clinical investigation

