The duration of the test periods ($35^{-1/3}$ days) and number of visits should be adequate to assess data on the skin condition of the subjects. The investigational products are tested for $35^{-1/3}$ days in each study period to ensure that the skin will have time to adjust to new conditions, reach a steady state, and for the subjects to test the product for an adequate number of days to give a thorough evaluation of the products.

To account for a possible carry-over effect, the steady state period of the treatment period begins after two weeks of product use. It is anticipated that the skin will have adapted to the new product after two weeks.

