10.3. Level of significance and power

A two-sided significance level of 5% will be applied. For a description of the power see section 10.2 above.

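### Does assuming 10 steady-state baseplates for both product types make the 83% power figure wrong for 1-piece and 2-piece users?

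*Combined protocol and SAP*

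**What the plan says.** Section 10.2 bases the sample size on a simplified linear mixed model without product type. It says "it is assumed that both 1- and 2-piece users uses approximately 10 baseplates in the steady state period", and then adds that power may favour 1-piece users if the two types are not combined, because they may use more products. On variability, "it is assumed that the total standard deviation of the primary endpoint is 1.1", split into 46% subject, 9% product-by-subject and 45% residual. The result for one type is that "33 subjects will ensure a power of 83% if the true difference is 0.3"; the same section gives 96% at 0.4. The types are to be evaluated separately within a combined model: "Hence 33, 1-piece and 33, 2-piece users will be needed to complete the study". If the types do not differ, the 66 are analysed together, with 82% power stated for a difference of 0.2.

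On product use, section 4.8 says "Subjects using 1-piece products are expected to change their products every day" and "Subjects using 2-piece products are expected to change their products every two-three days". It expects about 35 products per period for 1-piece users and about 20 baseplates per period for 2-piece users. Section 5.1 says "the steady state period of the treatment period begins after two weeks of product use", within a period of about 35 days.

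**The concern.** Ten baseplates is about half of what daily changing gives over three weeks, and it sits near the top of what a change every two to three days gives. So one power figure seems to be applied to two groups that will contribute quite different amounts of data. Section 10.1.2 estimates the product difference within each type and gives a single overall difference only if the product-by-type interaction is non-significant. If the results stay separate, a non-significant 2-piece result would be read against 83% power when the true figure might be lower, while 1-piece users would have power to spare. One could then ask for type-specific power figures, or for the 41/41 enrolment caps in section 6.2.1 to be moved towards 2-piece users.

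**Working it through.** **Inputs.** Total variance 1.1² = 1.21; product-by-subject share 9%; residual share 45%; 33 completers per type (all section 10.2). The subject component cancels in a within-subject comparison. For significance, "A two-sided significance level of 5% will be applied" (section 10.3).

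**Formula.** With m steady-state baseplates per product, the SD of a subject's difference in product means is

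SD = √[2 × 1.21 × (0.09 + 0.45/m)].

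The standard error is SD/√33. Power comes from the noncentral t distribution with 32 degrees of freedom and noncentrality difference/SE.

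**Reproducing the plan.** With m = 10, SD = √[2.42 × 0.135] = 0.572, SE = 0.572/√33 = 0.0995, and noncentrality is 0.3/0.0995 = 3.01. Power is 83.2%, against 83% stated. At 0.4 the same calculation gives 97.4%, against 96% stated (interpolated from a simulated table). The stated 83% is therefore correct for the assumption made.

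**Baseplate counts from the plan.** Steady state lasts 35 − 14 = 21 days.
- 1-piece, changed daily: 21.
- 2-piece, changed every three to every two days: 21/3 = 7 to 21/2 = 10.5 (8.4 at every 2.5 days).
- 2-piece, from the supply count of about 20 per period: 20 × 21/35 = 12.

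**Power with 33 completers, changing only m.**

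| Type | m | SD | Power at 0.3 | Power at 0.4 |
|---|---|---|---|---|
| Plan, both types | 10 | 0.572 | 83.2% | 97.4% |
| 1-piece | 21 | 0.519 | 89.6% | 99.0% |
| 2-piece | 7 | 0.611 | 78.1% | 95.4% |
| 2-piece | 8.4 | 0.589 | 80.9% | 96.6% |
| 2-piece | 10.5 | 0.567 | 83.8% | 97.5% |
| 2-piece | 12 | 0.556 | 85.3% | 98.0% |

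**Pooled analysis.** With 66 completers and a difference of 0.2, taking 21 baseplates for 1-piece and 7 to 10.5 for 2-piece, with equal weights for the types, gives 80.6% to 83.7%, against 82% stated.

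**Moving the caps.** Keeping 82 enrolled but splitting them 35/47 leaves 35 × 0.8 = 28 and 47 × 0.8 = 37.6, about 38, completers. If 1-piece users do change daily and 2-piece users change every third day, power at 0.3 is 83.8% in each type. If 1-piece users yield fewer scores, the 28 completers have 76.3% power at m = 10 and 70.7% at m = 7. With 33 completers those figures are 83.2% and 78.1%.

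**The case for a change.** The strongest case for a change is that the imbalance is predictable from the plan's own text. Section 4.8 states daily changing as the expectation for 1-piece users, so the plan could have quantified the caveat instead of only giving its direction. Under the stated frequencies the types differ by about 6 to 12 points (89.6% against 83.8% down to 78.1%), and no single figure describes both. The difference of 0.3 is also one that the plan itself chose to quote. A restated sentence would cost almost nothing.

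Those facts stand, but they do not show that the design falls short of what it claims. For 2-piece users, the assumed 10 lies within the 7 to 12 that the documents imply, and 83% lies within the resulting 78–85%. At worst, with every 2-piece user changing every third day, the stated figure is about 5 points too high. At 0.4 the lowest expected value is 95.4%, less than a point under the stated 96%. Power falls further, to 73% at 0.3, only if every 2-piece user changes every fourth day. That is the minimum accepted at entry (section 6.1.1), not what section 4.8 expects.

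Moving the caps is not a clear gain either. It spends the cautious 1-piece margin on the premise that every 1-piece user changes daily and every change is scored, and it departs from the equal split aimed for in sections 6 and 6.2.1.

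Section 4.8 also has a small internal mismatch: a change every two to three days over 35 days gives about 12 to 17.5 baseplates, not about 20. Power at either count stays within the 78–85% range, so this is clerical for the present purpose.

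**Conclusion.** No change to the plan is needed. The common value of 10 baseplates is a declared simplification whose direction the plan states. The 83% reproduces under it, is plausible for 2-piece users (78–85%) and is about 7 points conservative for 1-piece users (about 90%). At the difference of 0.4, both types have at least 95% power across the expected change frequencies, and pooled power at 0.2 stays close to the stated 82%. The requirement of 33 completers per type is not shown to be wrong. A reader who wants power by type can derive it from the inputs in sections 4.8, 5.1 and 10.2; stating it would change no sample size, analysis or pass criterion.

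The figures assume the same variance shares in both types, independent residuals within subject and product, a score at every change, and a 35-day period with the visit window ignored.
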